### 6.2 PREPARATION/HANDLING/STORAGE/ACCOUNTABILITY

#### 6.2.1 ACQUISITION AND ACCOUNTABILITY

The CRO 83Bar will handle all of the study materials, including Defined CBD and the placebo control. They will ship these materials directly to study participants.

#### 6.2.2 FORMULATION, APPEARANCE, PACKAGING, AND LABELING

The treatments will come in two independent blister packs labeled “Defined Research Treatment 1” and “Defined Research Treatment 2”. The blister packs contain a sufficient number of capsules for a total of 28 days of treatment (either Defined CBD or the Placebo Control).

#### 6.2.3 PRODUCT STORAGE AND STABILITY

The study treatment should be stored in a cool dry location, but do not require refrigeration.

#### 6.2.4 PREPARATION

The study treatments will require no preparation. The capsules are simply removed by the study participants from the blister packing before taking the treatment.

### 6.3 MEASURES TO MINIMIZE BIAS: RANDOMIZATION AND BLINDING

After enrollment, study participants will be assigned a study participant number, and will be randomized to receive Defined CBD or the Placebo control first. As Le Rêve 3.0 is a crossover study, participants who are randomized to receive Defined CBD as the first treatment will cross-over to receive the Placebo Control as the second treatment, and vice-versa. Both the study participants and the PI will be blinded to the study treatments. Unblinding will occur at the completion of the study by the PI. In certain rare instances (e.g. for a SAE), the blind may be broken for an individual participant by the PI.

### 6.4 STUDY INTERVENTION COMPLIANCE

Adherence to the protocol by study participants will be assessed by two independent approaches. In the first approach, a CBD Sleep Study team member will be checking Whoop data (stored on the cloud)

on a daily basis for each participant to ensure that the data is being collected consistently and accurately. In the second approach, study participants will be required to answer a text (SMS) message on a daily basis to confirm whether or not they took the study treatment.

## 6.5 CONCOMITANT THERAPY

Not applicable.

### 6.5.1 RESCUE MEDICINE

Not applicable.

## 7 STUDY INTERVENTION DISCONTINUATION AND PARTICIPANT DISCONTINUATION/WITHDRAWAL

### 7.1 DISCONTINUATION OF STUDY INTERVENTION

Discontinuation of the study intervention may occur in the event of a SAE if the medical monitor on the CBD Sleep Study Team makes that recommendation. In the event that the medical monitor determines that the study intervention should be discontinued for a study participant, they will prepare an electronic Case Report Form (eCRF) that will capture the date and the specific underlying reason for discontinuation of study intervention.

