### 5 STUDY POPULATION

#### 5.1 INCLUSION CRITERIA

In order to be eligible to participate in this study, an individual must meet all of the following criteria:

- 1) Has provided a signed and dated informed consent form.
- 2) Presence of chronic insomnia defined as self-reported difficulty initiating (latency to persistent sleep >30 min) and/or maintaining sleep (>30 mins awake during the middle of the night, or waking >30 mins before desired waking time on three or more nights per week) for at least 3 months.
- 3) Insomnia Severity Index score >15.
- 4) Male or female aged 25–70 years.
- 5) Is willing to comply with *all* study procedures throughout the entire study, including:
  - Wearing a sleep-tracking device on their wrist throughout entire clinical study.
  - Ensuring that the sleep-tracking device is connected to their smartphone via Bluetooth on a daily basis so that sleep data can be collected on a daily basis.
  - Ensuring that the sleep-tracking device is charged before going to bed each night, ensuring that sleep data can be collected on a daily basis.
  - Is willing to receive and respond to daily text (SMS) notifications for the duration of the entire clinical study.
  - During the treatment phases of the study, is willing to take the treatment for at least four nights in each week.
- 6) On the nights in which the participant takes the treatment, is willing to abstain from excessive alcohol intake (>two drinks/day).

7) On the nights in which the participant takes the treatment, is willing to refrain from drinking alcohol two hours before bedtime.

8) Female subjects who:

-Are postmenopausal, with amenorrhea for at least one year before the screening interview, OR

-Are surgically sterile, OR

-If of childbearing potential agree to practice effective double barrier methods of contraception (e.g., condom + diaphragm; condom or diaphragm + spermicidal gel or foam), from the time of the signing of informed consent through the last dose of study treatment, or agree to completely abstain from intercourse.

9) Self-reported bedtime between 9 pm and midnight on four-seven nights per week.

10) Owns a smartphone.

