- 19) Inability to refrain from use of any of the following contra-indicated drugs for at least one week prior to and for the duration of the study: erythromycin, clarithromycin, itraconazole, ketoconazole, posaconazole, voriconazole, ritonavir, telaprevir, boceprevir, amlodipine, gemfibrozil, cyclosporine, danazol, amiodarone, verapamil, diltiazem, rifampin, theophylline, tizanidine, bupropion, efavirenz, diflunisal, propofol, fenofibrate, lamotrigine, morphine, lorazepam, diazepam, clobazam, stiripentol, valproate, everolimus, sirolimus, or tacrolimus, niacin (vitamin B3 greater than 1g/ day), grapefruit juice.
- 20) Consumption of xanthine-containing beverages (i.e., tea, coffee, energy drinks or cola) of more than five cups or glasses per day.
- 21) Inability to refrain from greater than 400mg/day of caffeine consumption for study duration.
- 22) Participation in any other clinical trial within 30 days before the screening visit.
- 23) Night shift workers (during the 12 months prior to the study and during the study).
- 24) Individuals who nap three or more times per week over the preceding month.
- 25) Current delayed sleep phase syndrome where wake-up time is regularly (>5x/week) later than 9:00 a.m.
- 26) Individuals having to travel across more than two time zones or outside of their country of residence at any time during the study.
- 27) Females who are pregnant, are planning to become pregnant, or are breastfeeding.

28) History of allergies particularly to plant-based products containing terpenes, i.e. flavors and aromatic natural oils for example citrus, mango, lavender, thyme, cedarwood and pine products.

29) Known hypersensitivity to cannabinoids, including CBD.

30) Individuals may be excluded from participating in the study based on the investigator's professional judgement.

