### 7.2 PARTICIPANT DISCONTINUATION/WITHDRAWAL FROM THE STUDY

Study participants may voluntarily choose to withdraw from Le Rêve 3.0 at any point before or during the study by sending a text (SMS) message to [contact] or by sending an email to [contact]. If a study participant chooses to withdraw from the study for any reason, they will be required to disclose to the CBD Sleep Study Team the reason that they chose to withdraw. The PI may choose to withdraw a study participant(s) for significant study intervention non-compliance, or in the event of a SAE such that continued participation in the study would not be in the best interest of the participant. In the event that the PI chooses to withdraw a participant from the study, a member of the sleep study team will attempt to reach the participant by phone to inform them that they have been withdrawn from the study. The reason for participant discontinuation or withdrawal from the study will be recorded on the CRF. Subjects who sign the informed consent form, and are randomized and receive the study intervention, and subsequently withdraw, or are withdrawn or discontinued from the study, will not be replaced.

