### 8.3.8 EVENTS OF SPECIAL INTEREST

Events of special interest include all reports of medication error, abuse, misuse, overdose, and product complaints with AE. Medication error is any unintentional error in the prescribing, dispensing, preparation for administration or administration of an investigational product while the medication is in the control of a health care professional, patient, or consumer.

Medication errors may be classified as a medication error without an AE, which includes situations of missed dose; medication error with an AE; intercepted medication error, or potential medication error.

Abuse is defined as persistent or sporadic intentional excessive use of an investigational product by a participant.

Misuse is defined as any intentional and inappropriate administration of an investigational product that is not in accordance with the protocol instructions or the local prescribing information.

An overdose is defined as an accidental or intentional administration of a quantity of an investigational product given per administration or cumulatively which is above the maximum recommended dose as per protocol or in the product labelling (as it applies to the daily dose of the participant in question). In cases of a discrepancy in drug accountability, overdose will be established only when it is clear that the participant has taken the excess dose(s). Overdose cannot be established when the participant cannot account for the discrepancy except in cases in which the investigator has reason to suspect that the participant has taken the additional dose(s).

Product complaint is defined as complaints arising from potential deviations in the manufacturing, packaging, or distribution of the investigational product.

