### 8.3.9 REPORTING OF PREGNANCY

Not applicable.

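### Women of childbearing potential are enrolled, but the protocol states no question, report or stopping reason for a pregnancy that begins during the study

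*Combined protocol and SAP*

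**What the plan says.** **Entry.** Inclusion criterion 8 (section 5.1) admits women of childbearing potential who use double-barrier contraception or abstain, "from the time of the signing of informed consent through the last dose of study treatment". Exclusion criterion 27 (section 5.2) keeps out "Females who are pregnant, are planning to become pregnant, or are breastfeeding".

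**After entry.** Section 8.3.9 carries the heading "REPORTING OF PREGNANCY", and its whole content is that it does not apply. The schedule in section 1.3 places medical history at screening and has no pregnancy row. The recurring contact is a daily text. Section 6.4 uses it to confirm whether the dose was taken, section 10.1.7 for compliance and adverse event capture, and section 10.1.8 for missing device data.

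**Stopping.** Section 7.1: "Discontinuation of the study intervention may occur in the event of a SAE", if the medical monitor recommends it. Section 7.2: "The PI may choose to withdraw a study participant(s) for significant study intervention non-compliance, or in the event of a SAE". A participant may also withdraw by her own choice and must then give the reason.

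**Event definitions.** Pregnancy is not named among adverse events (8.3.1) or serious adverse events (8.3.2). Section 8.3.8 reads: "Events of special interest include all reports of medication error, abuse, misuse, overdose, and product complaints with AE".

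**The concern.** The entry criteria treat pregnancy as incompatible with receiving the study capsules, and they also admit women who could become pregnant. A pregnancy during the 12 weeks is therefore foreseeable, and marking its reporting as not applicable does not fit the population enrolled.

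Contraception makes pregnancy less likely but does not detect it. Followed as written, the plan could leave a participant who becomes pregnant taking capsules that she would have been refused at screening. Nothing prompts her to tell the team, no form is assigned to the information, and no rule says what happens next. What is at stake is participant safety and a complete exposure record. The primary comparison is not threatened.

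**Working it through.** The plan gives no figure to reproduce. The check sets the sections side by side and then counts days.

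**Would the team learn of a pregnancy?**
- Section 1.3: no pregnancy row after screening, and medical history is taken at screening.
- Sections 6.4, 10.1.7 and 10.1.8: the daily text covers doses, compliance, adverse events and device data. Pregnancy is not mentioned.
- Section 8.3.1: an unplanned pregnancy might be read as an unintended condition and so be volunteered as an adverse event, but the section does not say so.
- Section 10.1.10: a participant whose contraception fails while she follows criterion 8 has breached no stated duty, so the deviation route does not clearly reach her.

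**If the team learned of it, would a rule apply?**
- Section 7.1 names a serious adverse event. An uncomplicated pregnancy is not on the list in 8.3.2. Calling it medically important would take a case-by-case judgement.
- Section 7.2 names serious non-compliance with study treatment, or a serious adverse event. Section 6.4 treats compliance as dose-taking and device data, so pregnancy does not clearly meet it.
- Section 8.3.8 does not list pregnancy.

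**How long is the stretch without a stated question?** Inputs are from section 1.3: screening in weeks -4 to -1, enrolment on Day 1, dosing in weeks 3–6 and 8–11. Assume that Day 1 opens week 1, so screening falls 1 to 28 days before Day 1.

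| Event | Study day | Days after Day 1 | Days after screening |
|---|---|---|---|
| First planned dose (start of week 3) | 2 × 7 + 1 = 15 | 15 − 1 = 14 | 14 + 1 = 15 to 14 + 28 = 42 |
| Last planned dose night (end of week 11) | 11 × 7 = 77 | 77 − 1 = 76 | 76 + 1 = 77 to 76 + 28 = 104 |

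**With a question at the start of each dosing week.** The days are 15, 22, 29, 36, 50, 57, 64 and 71, which makes 8 questions. The longest gap from a question to a planned dose is 21 − 15 = 6 days. Daily texts over the study number 12 × 7 = 84. Even if all 150 participants were eligible for the item, there would be at most 8 × 150 = 1,200 answers. The true number is lower, because the item applies to women of childbearing potential.

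**Room for extra stops.** Section 9.2 plans 150 enrolled, at most 33% dropout and 100 needed: 150 × (1 − 0.33) = 150 × 0.67 = 100.5.

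**The case against.** **Sections 7.1 and 7.2 are permissive.** A reader might infer that dosing can stop for nothing except a serious adverse event, or that the investigator could not withdraw a pregnant participant. The text does not support that. Both sections say what may happen and bar no other reason. Section 7.1 goes on to provide for recording the specific reason whenever the medical monitor decides that treatment should stop. This objection stands: pregnancy is not named as a reason, but stopping for it is not forbidden.

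**The missing wording may exist elsewhere.** The consent form (10.1.1.1), the text-message wording and the call script (5.4) are outside the documents. Any of them could hold a pregnancy question or instruction. This limits the claim to the protocol. It does not alter the entry in 8.3.9 or put pregnancy into section 7.

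**No harm is shown.** The documents give no pregnancy rate and no reproductive risk figure, and the day counts measure calendar time, not risk. This is correct, so no injury or head count is claimed.

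**The barred drugs look like the same gap.** Exclusion 19 covers "Inability to refrain from use of any of the following contra-indicated drugs", and sections 2.3.1 and 8.2.4 extend the bar through the study, while section 6.5 on concomitant therapy is marked not applicable. A reader might infer that new use of a listed drug would go equally unhandled. It would not. Such use breaches the protocol and falls under the deviation duty in 10.1.10. Knowing use alongside the capsules is arguably misuse under 8.3.8. The daily compliance and adverse event texts could bring it to light, and 7.2 arguably allows withdrawal. What remains is missing detail in 6.5.

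**Conclusion.** The pregnancy point holds. The entry in 8.3.9 is wrong for a trial that enrols women of childbearing potential. As far as the protocol states, nobody asks about pregnancy between screening and a last planned dose 77 to 104 days later, and no written rule requires study treatment to stop if a pregnancy is reported. It should be corrected, although the contraception requirement and voluntary withdrawal lower the risk.

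The conclusion rests on the protocol text alone and on reading section 1.3 with Day 1 as the start of week 1. If the consent form or texts already ask about pregnancy, the detection part shrinks to a cross-reference, but the correction to 8.3.9 and the stopping reason in 7.1 are still needed. The drug issue is no more than a wording note on section 6.5.

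**What to change.** 1. **Section 8.3.9:** replace the current entry with an instruction that participants report a pregnancy at once and that it is recorded on the eCRF.
2. **Daily text:** for women of childbearing potential, add a pregnancy item before the first dose of each treatment period (weeks 3 and 8) and weekly during dosing. Inclusion criterion 5 already secures the channel: "Is willing to receive and respond to daily text (SMS) notifications for the duration of the entire clinical study".
3. **Section 7.1:** state that a participant who becomes pregnant stops study treatment and is followed by the medical monitor.
4. **Section 6.5 (minor):** replace the not-applicable entry with a pointer to the study-long drug bar. A weekly question on the full exclusion 19 list is not advised. The list has 36 items, including grapefruit juice, which sections 2.3.1 and 8.2.4 omit. Nor is an automatic stop pending review advised, because it would have no defined end.

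**Cost.** Up to 8 extra text items per eligible participant, an amendment and revised participant materials for IRB review with a decision on re-consent (Statement of Compliance), and monitor follow-up of any pregnancy. A rare extra treatment stop is possible. If it came on top of the full 33% dropout, completers could fall below 100, since the plan leaves 100.5. That margin is not a reason to keep dosing a pregnant participant. Self-report will still miss a pregnancy that the participant has not recognised.

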### 7.2 PARTICIPANT DISCONTINUATION/WITHDRAWAL FROM THE STUDY

Study participants may voluntarily choose to withdraw from Le Rêve 3.0 at any point before or during the study by sending a text (SMS) message to [contact] or by sending an email to [contact]. If a study participant chooses to withdraw from the study for any reason, they will be required to disclose to the CBD Sleep Study Team the reason that they chose to withdraw. The PI may choose to withdraw a study participant(s) for significant study intervention non-compliance, or in the event of a SAE such that continued participation in the study would not be in the best interest of the participant. In the event that the PI chooses to withdraw a participant from the study, a member of the sleep study team will attempt to reach the participant by phone to inform them that they have been withdrawn from the study. The reason for participant discontinuation or withdrawal from the study will be recorded on the CRF. Subjects who sign the informed consent form, and are randomized and receive the study intervention, and subsequently withdraw, or are withdrawn or discontinued from the study, will not be replaced.

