## 4 STUDY DESIGN

### 4.1 OVERALL DESIGN

We hypothesize that Defined CBD, a novel CBD-based formulation in the form of a small orally administered capsule, will increase the percentage of time participants spend in deep (SWS) and REM sleep, as measured by an objective sleep-tracking device called “Whoop”. Our research study, entitled Le Rêve 3.0, is a double-blind, placebo-controlled, randomized, crossover investigational study to determine if Defined CBD, a Custom-Formulated CBD Capsule, influences sleep physiology. This capsule contains no Δ-9-THC. As this study is only designed to evaluate the effects of Defined CBD on the structure and function of sleep physiology, the phase of the trial is not applicable. This trial is not intended to treat, diagnose, prevent, or cure any disease.

The Le Rêve 3.0 study will involve a cross-over design in which study participants will cycle through two independent treatments, each for four weeks (Treatment 1: Placebo; Treatment 2: Defined CBD). The placebo will look, smell and taste the same as the Defined CBD capsule. The study participants will initially be randomized with respect to the treatment arm, and every participant will cycle through both treatment arms. We will use a double-blind design in which the investigator and study participants will both be blinded to the treatments. Baseline data for each participant will be collected for two weeks prior to initiating treatments, as well as for a one-week washout period following each treatment arm. The entire study duration will be 12 weeks (for Schema see section 1.2).

Primary data for Le Rêve will be obtained in a completely unbiased manner from a non-invasive sleep-tracking wrist-worn device called “Whoop” (<https://www.whoop.com>), that electronically collects and transmits sleep data from study participants in the comfort of their own beds.

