#### 6.1.2 DOSING AND ADMINISTRATION

The dose participants will take in the study is two small capsules, that contain a total of 300 mg CBD and 8 mg of terpenes (1 mg each of the terpenes linalool, myrcene, phytol, limonene,  $\alpha$ -terpinene,  $\alpha$ -terpineol,  $\alpha$ -pinene, and  $\beta$ -caryophyllene) that will be taken orally with a glass of water one hour before bedtime. The participants will be required to take the study medication on a minimum of four nights per week for each of the four-week treatment phases of the study.

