## 9.2 SAMPLE SIZE DETERMINATION

A total of 100 participants will provide at least 90% power to detect a 15% difference in the percentage of time participants spend in deep and REM sleep, as quantified using the Whoop sleep-tracking device after the four-week treatment phase. The CRO 83Bar will recruit 8,000 potential study participants using social media, will screen approximately 800 study participants via online screening surveys, will contact 440 participants from a call center, and will ultimately enroll 150 qualified study participants. Based on our two previous clinical studies with Defined CBD, we anticipate a maximum dropout rate of 33% in Le Rêve 3.0.

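### Section 7.2 lets the investigator withdraw participants from the study for poor compliance after randomisation, with no link to the four-night standard and no provision to keep collecting data

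*Combined protocol and SAP*

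**What the plan says.** Section 7.2 gives the investigator two grounds for removing someone from the study: an SAE that makes continuing unwise, and poor compliance. On the second it reads "The PI may choose to withdraw a study participant(s) for significant study intervention non-compliance". The participant is then told that they are out of the study. Participants who have been randomised and treated and who later "are withdrawn or discontinued from the study, will not be replaced".

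Stopping capsules is a separate act, in section 7.1, and is described for one situation only: "Discontinuation of the study intervention may occur in the event of a SAE", on the medical monitor's recommendation.

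The compliance standard is in section 6.1.2 (and section 5.1, item 5): participants are "required to take the study medication on a minimum of four nights per week". Section 6.4 monitors compliance in two ways. Staff check the Whoop data each day, and "study participants will be required to answer a text (SMS) message on a daily basis to confirm whether or not they took the study treatment". Section 7.2 does not refer to either section when it speaks of significant non-compliance.

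The design is a two-period crossover in which, according to section 4.1, "every participant will cycle through both treatment arms". Section 9.4.2 compares the two treatments at the end of the two four-week phases. Section 9.3 gives the timing of the analysis and a safety dataset, but no efficacy population. On numbers, section 9.2 says "we anticipate a maximum dropout rate of 33"%.

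**The concern.** Capsule-taking is an outcome of being randomised and treated. Someone who feels unwell on the capsules, or who notices no benefit, may take fewer of them. If that person is then removed from the study, the participants who remain are partly selected by how they responded. The comparison moves from the effect in everyone randomised towards the effect in those who kept taking capsules.

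A crossover is sensitive to this because each participant's contribution rests on two periods. A person removed in period 1 never supplies period 2. Defining an all-randomised analysis set later would not restore nights that were never recorded.

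The loss is largely avoidable. Sleep is measured by a wrist device that participants agree to wear for the whole study (section 5.1, item 5), and the measurement does not depend on whether a capsule was taken that night.

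**Working it through.** **1. What follows from the rule as written.** The treatment weeks come from the schedule of activities (section 1.3).

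| Time of withdrawal | Period 1 data | Period 2 data | Complete pair? |
|---|---|---|---|
| Weeks 3–6 (period 1) | partial | none | no |
| Week 7 (washout) | complete | none | no |
| Weeks 8–11 (period 2) | complete | partial | no |
| Week 12 (final washout) | complete | complete | yes |

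Two steps here are inferences. The documents do not say in words that data collection ends at withdrawal. That follows from the participant having left the study and from the absence of any follow-up rule in sections 7.1, 7.2 and 8.1. They also do not say how one-period participants are treated. Sections 9.4.1 to 9.4.3 specify a two-sided test at 0.05 without naming it. A mixed model could use a single period, but none is specified.

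**2. The plan's own figure.** Section 9.2 needs 100 participants, allows at most 33% dropout and enrols 150.

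- 100 / (1 − 0.33) = 149.3, rounded up to 150. The enrolment figure reproduces.
- 150 × 0.67 = 100.5 remaining.

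Section 9.2 does not say whether withdrawals by the investigator count within the 33%. If they do, the planned number is unaffected.

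**3. Extreme-case size of the selection.** Let p be the share of participants removed, E the mean effect in those kept, and zero the effect in every participant removed.

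- Effect in all randomised = (1 − p) × E + p × 0 = (1 − p) × E.
- Ratio of the reported to the all-randomised effect = E / [(1 − p) × E] = 1 / (1 − p).
- p = 10% (15 of 150): 1 / 0.90 = 1.11, an overstatement of 11%.
- p = 20% (30 of 150): 1 / 0.80 = 1.25, an overstatement of 25%.

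Both values of p, and the zero effect, are assumptions. The documents give no figure for either.

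**The case against.** The strongest reply is that this is a discretionary rule with several safeguards around it. The investigator is blinded (section 6.3), so removal cannot be steered by arm. Each participant is their own control. The rule says that the investigator may act, and only on significant non-compliance, so not every poor complier will go. The four-night standard does exist, and the 33% allowance may already contain these losses.

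Much of this stands. Blinding limits deliberate selection, but it does not prevent selection that works through adherence itself. The four-night standard is stated; the gap is that section 7.2 does not use it. The allowance covers how many are lost, not which ones.

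Three stronger readings are tempting and are not supported:

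- **Power falls below 90%.** A reader might subtract these withdrawals from the planned 100. Section 9.2 presents 33% as a maximum and does not exclude investigator withdrawals from it. It also gives no standard deviation, so any standardised effect used for such a calculation would have to be back-solved.
- **The estimate becomes one for compliers only, inflated by 1/(1 − p).** This needs all poor compliers to be removed and each to have exactly zero effect. Someone taking capsules three nights a week need not have zero effect, and for someone removed while on placebo the effect of the active capsules is unknown.
- **The non-compliance ground should simply be deleted.** Section 8.3.8 describes misuse, abuse and overdose. These can occur without an SAE, and the other ground in section 7.2 requires one. Outright deletion could therefore reach safety decisions.

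Non-compliance is also not only about capsules. Sections 6.4 and 10.1.8 include missing device data, and for a participant who does not wear the device, continued follow-up recovers little.

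**Conclusion.** The concern holds as a weakness in a stated rule that should be corrected. Section 7.2 permits removal from the study for a post-randomisation behaviour, at discretion and without a linked threshold. Nothing elsewhere in the plan keeps the data coming or says how an incomplete pair is analysed. Following the rule can cause avoidable and possibly selective loss of pairs.

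Its actual size is unknown, because neither the frequency of such withdrawals nor the direction of any bias can be derived from the documents. The 11% and 25% figures mark an extreme case under assumed inputs and are not estimates. The conclusion rests on reading withdrawal from the study as the end of data collection, and on adherence being related to tolerability or perceived benefit. The first is the natural reading; the second is plausible but not shown.

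**What to change.** In section 7.2, state that missed or stopped capsules alone do not end study participation or data collection. Such participants keep wearing the device and answering SMS messages and surveys to week 12, unless they withdraw consent.

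In sections 9.3 and 9.4, state that they are analysed by randomised sequence with all available period data, using a method that accepts participants with one period. Report an analysis of compliant participants, defined by the existing standard of at least four nights per week, as supportive only.

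Leave all decisions on stopping capsules unchanged, along with all safety-related withdrawal, including for misuse or overdose.

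The cost is protocol wording and some retention effort, for which the automatic reminders in section 10.1.8 already exist. Continued wear, charging and SMS replies are a small burden, but participants accept them for the whole study at entry. The headline effect may be somewhat smaller once poor compliers are included. The change is best made before enrolment starts, because unrecorded nights cannot be recovered.
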